#### **Statistical Analysis**

Basic descriptive statistics (mean and standard deviation) were analyzed for femoral head center displacement from the acetabulum center for both implanted (post-operative) and non-implanted (normal, pre-operative) cases. This was evaluated for one complete gait cycle for each subject.

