**BIG ORANGE. BIG IDEAS.** Flagship Campus of the University of Tennessee System **ur** 

# In vivo determination of THA kinematics and sound for normal, diseased and implanted hips

[name] University of Tennessee [name] [contact] [contact] Email: [contact]

In vivo kinematics and acoustics will be assessed for 20 subjects for this study: 10 normal hips and 10 ten hips will be diseased, requiring a THA and then those same ten diseased hips will be reanalyzed at least six months post-operative after implantation of a THA manufactured by DePuy Synthes by [name] of Northside Hospital Forsyth [[name]]: this is the location from which all study participants will be recruited. Ten subjects will be implanted with a similar surgical technique and will be implanted with either a Summit/Pinnacle THA or Corail/Pinnacle THA. All THAs should be judged clinically successful (Harris Hip Scores HHS> 90 points), without pain, functional deficits, or generalized inflammatory. All subjects must have demonstrated no evidence of post-operative hip subluxation or dislocation. The remaining ten subjects will have normal hips. None of the subjects can walk with a detectable limp and all subjects must be able to actively abduct their operated or healthy hip against gravity without difficulty.

Deciding which patients receive which of the two kinds of implants is up to the discretion of [name], according to his professional opinion. The determination as to which type of implant patients receive is outside the scope of this particular study. Participation in the study is entirely voluntary, and the patient's decision as to whether or not to participate will not impact the type or quality of care provided by the surgeon or his staff.

We will use the following inclusion criteria to recruit participants for the diseased/implanted cohort of this study:

- 1. Subjects will require a THA and will be implanted with either Summit/Pinnacle THA or Corail/Pinnacle THA by [name].
- 2. For Phase 2, subjects must be at least six months post-operative with no other surgical procedures conducted within the past six months that will prohibit them from performing the study activities.
- 3. Subjects must be between 40-85 years of age.
- 4. Potential subjects will have a body weight of less than 250 lbs.
- 5. Participants must have Body Mass Index (BMI) of less than 38.

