#### Procedures

## **Computer Tomography**

Since the normal and diseased, pre-operative hip subjects will undergo a computer tomography (CT) scan of the hip so researchers can create the bone models necessary to analyze the hip data acquired after the fluoroscopy collection. These normal and pre-operative bone models will be compared to the computer-aided designed (CAD) bone models created from data acquired from DePuy's implant-specific information (size, reference and lot numbers), all of which will be used in the analysis of the fluoroscopy and sound data obtained during data collection.

The CT scans for the normal subjects and diseased/pre-operative THA patients will take place at Northside Hospital Forsyth [[name]] six inches distally on the femur and six inches proximally on the pelvis. The study will be submitted to Northside Hospital's Institutional Review Board for review and approval. After CT scans have been conducted, they will be provided to UT researchers by mail/courier or secure electronic transfer to CMR researchers.

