## Fluoroscopy Data Collection at the University of Tennessee

Subjects with a normal hip will travel to Knoxville for the fluoroscopy/sound data collection one time, while subjects with a diseased and then implanted hip will travel to Knoxville for data collection twice, once pre-operatively and a second time at least 6 months post-operatively.

In addition to fluoroscopy video, subjects will be videotaped from the torso down (to maintain patient anonymity) while performing the activities (live feed perspective). The speed level of each trial will be based on the comfort level of the subject. Activities will be performed without the aid of handrails; however, one of the researchers will be ready and in close proximity to assist each patient in case the participant requires help. This precaution will be practiced for all participants, regardless of physical wellbeing, age or prior results; no assumptions will be made as to any participant's capabilities.

Subjects will be video-recorded from the waist down while performing the activities while under fluoroscopy surveillance. The speed level of each trial will be based on the comfort level of the patient. The fluoroscopic images will be stored digitally for subsequent analysis on secure servers and workstations at UT. In vivo hip kinematics will be assessed for all 10 normal subjects, the 10 diseased hip/pre-operative subjects who will be assessed again after they have been implanted with THA at least six months post-operatively.

On the day of data collection, there will be at least three UT researchers present to conduct the fluoroscopic evaluations, as well as a State of Tennessee or ARRT certified Radiation Technician (RT) to run the x-ray component of the machine. These three UT researchers, graduate research assistants (GRAs), will be appointed by either Drs. [name] or [name] and will have significant experience with this particular tracking fluoroscope system (TFS).

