## Phase 2: Post-Operative Fluoroscopy data collection

For Phase 2 of the study, only seven of the ten hips that were diseased and required a THA that participated in Phase 1 of the study in Knoxville were reachable to participate in post-operative fluoroscopy at Abercrombie. Radiology in Knoxville, TN Weisgarber Medical Center, [name].

The following inclusion criteria were used to ensure hip subjects that participated in Phase 1 meet eligibility for continuing participation in Phase 2:

- 1. Subjects required a THA and were implanted with either Summit/Pinnacle THA or Corail/Pinnacle THA by [name].
- 2. All subjects are well past the required six months post-operative time.
- 3. Subjects must be between 40-85 years of age.
- 4. Potential subjects will have a body weight equal to or less than 300 lbs.
- 5. Participants must have Body Mass Index (BMI) of less than 40.
- 6. Potential subjects' THAs should be judged clinically successful with a HHS >90.
- 7. Participants must be able to walk on level ground without assistance.
- 8. Subjects from the physician's list who do not meet the study requirements will not be considered.
- 9. Subjects must be willing to sign the Informed Consent (IC)/HIPAA form to participate in the study.

To ensure that all subjects who participated in Phase 1 of the study still met all study eligibility requirements prior to undergoing the post-operative fluoroscopy procedure, a subject specific form was completed for each of the subjects prior to contact for scheduling of post-operative fluoroscopy visit. [name] office staff will be responsible for reviewing the medical files of the subjects that participated in Phase 1 and using the checklist to ensure all subjects meet study criteria. If subjects meet the criteria, they will then be contacted by [name] office to inform the subjects that the second phase of the study is underway and to schedule their appointments to Abercrombie Radiology in Knoxville.

The same reimbursement of travel expenses applied to Phase 2 as was in place for Phase 1. To facilitate implanted subject post-operative participation and compensate for the delay between data collections, the stipend for the implanted group was increased.

Due to protocol revisions (only performing gait activity), change in post-operative fluoroscopy

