data collection location (Abercrombie Radiology instead of UT campus), and increase in stipend, each subject will be consented again by UT researchers so subjects are aware and understand the changes to the study. After signing the revised IC form, s/he will be fitted with non-invasive, surface-based sound/vibration sensors placed at the closest distance to the hip joint interface, allowing for the capturing of sound emissions during the gait activity. The sensor will be securely attached using a spica dressing, a tight-fitting, sleeve-like article of clothing, designed for the purpose of the study, and adjusted to subject size using integrated Velcro strips. The sensors will be connected to a data acquisition system that will also be connected to the subject by thin, ultra-lightweight cables while s/he performs the level walking (gait) activity.

In addition to fluoroscopy video, subjects will be videotaped from the torso down (to maintain subject anonymity) while performing the activity (live feed perspective) under fluoroscopy surveillance. The speed level of each trial will be based on the comfort level of the subject. The activity will be performed without the aid of handrails; however, one of the researchers will be ready and in close proximity to assist each subject in case the participant requires help. This precaution will be practiced for all participants, regardless of physical wellbeing, age or prior results; no assumptions will be made as to any participant's capabilities.

In vivo hip kinematics will be assessed for all 10 normal subjects, 10 diseased hip/pre-operative subjects and the same 10 subjects will be assessed again after they complete the post-operative

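### The plan summarises displacement by state only, with no within-hip post-minus-pre change, although the same diseased hips are measured twice and at most seven of ten were reachable for the second measurement

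*Combined protocol and SAP*

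**What the plan says.** The Statistical Analysis section has two sentences. The first reads, in part, "Basic descriptive statistics (mean and standard deviation) were analyzed for femoral head center displacement from the acetabulum center", for implanted (post-operative) and non-implanted (normal, pre-operative) cases. The second adds: "This was evaluated for one complete gait cycle for each subject". It gives no n for any state, no single value per hip, no post-minus-pre difference, and no rule for hips without a second measurement.

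The design is nevertheless a repeated one. The opening section says that "those same ten diseased hips will be reanalyzed at least six months post-operative". The section on fluoroscopy data collection at the University of Tennessee describes the ten pre-operative subjects as those "who will be assessed again after they have been implanted with THA at least six months post-operatively".

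The Phase 2 section gives two numbers for the second measurement. It reports that "only seven of the ten hips that were diseased and required a THA" and had taken part in Phase 1 were reachable. Further on it still says "the same 10 subjects will be assessed again after they complete the post-operative", where the sentence breaks off in the copy available. Phase 2 also has its own eligibility criteria, including a Harris Hip Score (HHS) above 90, so seven is an upper limit.

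**The concern.** When the same hips are measured before and after surgery, the direct descriptive summary is the change in each hip. Means and SDs by state do not supply it, for two reasons.

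- **Different hips may be compared.** If the pre-operative mean uses all ten hips and the post-operative mean at most seven, the gap between them mixes change after THA with who came back. The plan does not say which hips enter the pre-operative figure.
- **The spread of change is lost.** Two group SDs do not determine the SD of the change, because that depends on the pre/post correlation, which is not reported.

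A more basic gap lies beneath both. One gait cycle yields a series of displacement values. Unless one value per hip is named, the SD could describe variation between hips or within a cycle.

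What is at stake is how the pre/post figures are read. With no test and no sample-size calculation in the plan, power and error rates do not come into it.

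**Working it through.** The plan has no figure of its own to reproduce: it states no SD, effect size, alpha or power. The documents give no displacement data, so results are in units of s, the pre-operative between-hip SD.

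**Inputs from the documents:** 10 diseased hips (opening section); at most 7 reachable for Phase 2, so at least 3/10 = 30% have no second measurement (Phase 2 section).

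**Assumptions:** all 10 pre-operative and 7 post-operative hips are used; for steps 2 to 4, pre and post SDs are equal and the pre/post correlation is r.

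**1. Shift from unequal groups.** Subtract the paired change in the seven from the 10-versus-7 difference:

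[post(7) − pre(10)] − [post(7) − pre(7)] = pre(7) − pre(10) = 0.3 × [pre(7) − pre(3)]

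- A retained-versus-lost gap of 0.5 s gives 0.3 × 0.5 = 0.15 s; a gap of 1 s gives 0.30 s.
- Upper bound: the sum of squares between the two subsets is (7 × 3/10) × gap² and cannot exceed the total, 9 s². So gap ≤ √(9/2.1) = 2.07 s and shift ≤ 0.3 × 2.07 = 0.62 s.
- If the three were lost purely at random, the SD of the shift is s × √[(1/7)(1 − 7/10)] = 0.21 s.

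**2. SD of the within-hip change** = s × √[2(1 − r)]:

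| r | SD of change |
|---|---|
| 0.3 | 1.18 s |
| 0.5 | 1.00 s |
| 0.7 | 0.77 s |
| 0.9 | 0.45 s |

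Over this range the group SDs leave open a factor of 1.18/0.45 = 2.6.

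**3. Width of a 95% CI for the mean change, if one is added.** The half-width in SDs of the change is t(0.975, n − 1)/√n: 1.24 for n = 5, 1.05 for n = 6, 0.92 for n = 7, and 0.72 for n = 10 (the other number in the Phase 2 section).

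**4. Paired against unpaired precision.**

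- Paired, n = 7: 2.447 × √[2(1 − r)/7] = 1.09 s, 0.92 s and 0.72 s at r = 0.3, 0.5 and 0.7.
- Unpaired, 10 versus 7: 2.131 × √(1/10 + 1/7) = 2.131 × 0.493 = 1.05 s, whatever r is.
- The two are equal at r = 0.355. Below that, the paired interval is the wider one.

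**The case against.** The strongest reply is that nothing in the plan is contradicted. The title speaks of determining kinematics and sound for normal, diseased and implanted hips, no within-hip objective is stated, and describing three states fits that aim. This stands as far as it goes: the analysis is not invalid. A within-hip change is equally descriptive, however, and it is the summary for which the repeated measurement is suited.

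Second, the 10-versus-7 mismatch is conditional. The pre-operative summary might already be restricted to hips that returned. That is true, and the shift in step 1 applies only if it was not. Even with the same seven hips at both times, the SD of the change could not be recovered.

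Third, the later mention of 10 subjects is probably leftover planning text in a truncated sentence, and eligibility was checked before subjects were contacted, so the seven may already have passed screening. Both points are fair. They make 7 the likelier figure, and nothing in the documents supports 5 or 6 specifically. The actual n still has to be stated.

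Fourth, every size quoted rests on an assumed correlation or gap, and on equal SDs where these enter; the 0.62 s bound needs hips that do not vary within each subset; and pairing may not improve precision. All of this is conceded, and the case does not depend on a precision gain.

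Fifth, a paired change is itself hard to interpret, and three lost hips against seven retained can show little. This stands as a limit on interpretation. The same difficulties affect the comparison of group means.

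Finally, the sections on recruiting normal-hip subjects and on medical record data mention correlating clinical outcomes with kinematic results. That is some analysis intent outside the Statistical Analysis section, but it supplies no pre/post change.

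**Conclusion.** The concern holds. The stated analysis does not report within-hip change and does not say which or how many hips contribute to each state. If 10 pre-operative hips are set beside 7 post-operative hips, the difference departs from the paired change by 0.3 times the retained-versus-lost gap, typically about 0.21 s under purely random loss. The spread of individual change stays undetermined in any case. These sizes are illustrations under the stated assumptions, not estimates from the trial.

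This is a worthwhile and cheap improvement to a descriptive analysis, not a fatal flaw. Whether normal and pre-operative hips share one non-implanted mean is unclear from the text; that is a point to clarify and is not claimed as an error here.

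**What to change.** First reconcile the 7 and the 10 in the Phase 2 section and state the actual n for each state. Then:

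1. Name one summary value per hip, for example the maximum femoral head centre displacement over the analysed gait cycle, which fits the reading of frames for sliding or separation described under Fluoroscopy Activity. If another value has already been used, name that one.
2. Give the between-hip mean and SD separately for normal, pre-operative and post-operative hips, each with its n.
3. For hips measured at both times, list the individual pairs and give the mean and SD of post-minus-pre displacement, optionally with a 95% CI.
4. Show pre-operative displacement and pre-operative HHS, which is already collected, side by side for retained and lost hips.

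The text should say that the change describes only retained hips meeting the Phase 2 criteria, including HHS above 90. It should also say that the change may include differences between CT-based and CAD-based models (the Computer Tomography section says "These normal and pre-operative bone models will be compared to the computer-aided designed (CAD) bone models") and from the new collection site recorded in the Phase 2 section. If the analysis is already done, as its past tense suggests, the paired summary should be labelled post hoc.

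The cost is a few sentences and one small table, with no new data. The downside is a wide interval, about 0.92 SDs of the change either side with seven pairs. Pairing removes the 10/7 mismatch but not the selection of retained, clinically successful hips, nor any model or site difference.

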#### BENEFITS

The potential benefits from this study include, but are not limited to:

- Subject stipend
- Better understanding of the joints analyzed with the same technique in the past.
- Future implant design improvements based on the kinematic findings.
- New and advanced surgical techniques for THA based on the results.
- There are no direct health benefits to participants of the study.

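### Only a mean and SD are planned, so the comparisons of diseased and implanted hips with normal hips get no estimate or precision; with about 10 versus 7 hips, similar means would not show similarity

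*Combined protocol and SAP*

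**What the plan says.** The opening paragraph under the study title sets the groups: "In vivo kinematics and acoustics will be assessed for 20 subjects for this study: 10 normal hips and 10 ten hips will be diseased", with the diseased hips measured again at least six months after THA.

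The whole statistical plan is the Statistical Analysis section. Its method is "Basic descriptive statistics (mean and standard deviation) were analyzed for femoral head center displacement from the acetabulum center", given "for both implanted (post-operative) and non-implanted (normal, pre-operative) cases". The unit of observation is set by "This was evaluated for one complete gait cycle for each subject". The text available for review contains no between-group difference, confidence interval, test, equivalence margin or sample-size rationale.

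The number of implanted hips is stated in two ways, both in the Phase 2 section. Near its start, "only seven of the ten hips that were diseased and required a THA that participated in Phase 1" could be reached for the post-operative visit. Near its end, "the same 10 subjects will be assessed again after they complete the post-operative" data collection.

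Among the potential benefits, the Benefits section lists "Future implant design improvements based on the kinematic findings".

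**The concern.** Ten people with healthy hips undergo CT and fluoroscopy, and the title names normal, diseased and implanted hips together. The natural use of the normal group is as a reference, so readers will set the other two groups against it. With only group means and SDs, they would do that by eye.

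Two things can then go wrong. First, similar means for normal and implanted hips could be taken as a sign that the implanted hip moves like a normal one, when so few hips leave a large difference open. Dissimilar means could equally be chance. Second, if all non-implanted hips are summarised together, no comparison with normal can be recovered from the report.

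This point concerns the comparisons with normal hips. The within-hip change from before to after surgery is a separate, paired question.

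**Working it through.** The plan states no precision, power, SD or confidence level, so there is no figure of its own to reproduce.

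**Inputs**
- Normal hips: 10. Diseased hips: 10 (opening paragraph).
- Implanted hips: 7 (start of the Phase 2 section).
- One gait cycle per subject (Statistical Analysis), so the sample size is the number of hips.
- Assumed: two-sided 95% level, independent groups, approximate normality and, at first, a common between-hip SD. Results are in SD units because the documents give no SD in millimetres.

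**Half-width with a common SD:** t(0.975, n1 + n2 − 2) × √(1/n1 + 1/n2)
- Normal versus diseased, 10 versus 10: √(1/10 + 1/10) = 0.447; times t on 18 df (2.101) = **0.94 SD**.
- Normal versus implanted, 10 versus 7: √(1/10 + 1/7) = 0.493; times t on 15 df (2.131) = **1.05 SD**.

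With identical observed means, the second interval runs from −1.05 to +1.05 SD, which just fails to exclude 1 SD. For 10 versus 10, a 1-SD difference is excluded in both directions only if the observed difference is below 1 − 0.94 = 0.06 SD.

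**Sensitivity for 10 versus 7**
- Normal approximation: 1.96 × 0.493 = 0.97 SD.
- Welch, equal SDs: 1.06 SD.
- Welch, implanted SD half the normal SD: √(1/10 + 0.25/7) = 0.368; times t on 13.9 df = 0.79 normal SDs.
- Welch, implanted SD twice the normal SD: √(1/10 + 4/7) = 0.819; times t on 8.1 df = 1.88 normal SDs.

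Seven hips cannot settle which of these applies. Under normality, the 95% limits for their SD are √(6/14.45) = 0.64 to √(6/1.237) = 2.20 times the estimate.

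**Effect of the conflicting n.** A reader who takes the implanted group to be ten would work with 0.94 SD. At seven it is 1.05 SD, about 12% wider (1.05/0.94 = 1.12).

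**Effect of pooling.** Write N, D and I for the normal, diseased and implanted means. A pooled non-implanted mean of 10 and 10 hips is (10N + 10D)/20 = (N + D)/2. The report would then give I and (N + D)/2, from which neither N − D nor N − I can be obtained.

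**The case against.** The strongest reply is that this is a small descriptive study and calls itself one. It states no hypothesis, test or equivalence aim, and the line on implant design is a general statement of benefit. A reader might infer that the study sets out to show, or will report, a return to normal mechanics. The documents do not say so. That stands: the risk lies in how the output could be read.

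A second reply is that anyone given n, mean and SD for each of the three groups can compute the unpaired intervals. That also stands, but only if the three groups are reported separately with their true n. The wording leaves the first open, and the Phase 2 section contradicts itself on the second. Three summaries would still hide whether one hip drives a group's mean and SD.

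A third reply is that an interval does not make the groups comparable. This is correct. Normal subjects are aged 18 to 65 and surgical subjects 40 to 85. Implanted hips must have a Harris Hip Score above 90. The post-operative imaging was moved to another site. Normal and pre-operative hips use CT bone models, while implanted hips rest on the manufacturer's CAD data. An unadjusted interval covers sampling error alone, so the fix has to say so.

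Finally, displacement is a distance, and one might suppose that it is right-skewed. The documents give no data on this. It is a reason to show individual values, not an established fault of the mean and SD.

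**Conclusion.** The concern holds in a limited form. The plan gives no estimate or precision for either comparison with normal hips, and its wording permits a summary from which neither could be recovered. Under the stated assumptions the uncertainty is about one between-hip SD either way: 0.94 for normal versus diseased and 1.05 for normal versus implanted, the latter ranging from 0.79 to 1.88 normal SDs with unequal spread. Similar means would not be evidence of similarity.

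A firmer statement, that a 1-SD difference cannot be excluded, should not be made in general. With equal means it holds only for 10 versus 7, by a narrow margin (1.05 against 1.00), and it fails under the normal approximation (0.97) or a much smaller implanted SD. Nor do the documents say what 1 SD is in millimetres or what displacement matters clinically. Pooling of normal and diseased hips is a possible reading, not a demonstrated one. Seven is the number who could be reached. Eligibility was still to be checked, so the number analysed needs confirming.

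This is an inexpensive improvement that should be made. It does not invalidate the descriptive summaries.

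**What to change.** Amend the Statistical Analysis section as follows.

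1. Summarise normal, pre-operative and post-operative hips as three separate groups, each with the number actually analysed. Reconcile seven and ten in the Phase 2 section.
2. Define one value per hip before the groups are compared, for example the maximum displacement over the gait cycle. Displacement varies through the cycle, and the present text does not say which value enters the mean. The section is written in the past tense, so if results have already been seen, say that the definition was chosen afterwards.
3. Report normal minus pre-operative and normal minus post-operative mean differences with Welch 95% intervals, and a permutation analysis as a check on the normality assumption.
4. Plot every hip's value by group.
5. State that overlapping means or SDs will not be read as equivalence to normal.
6. State that the intervals cover sampling error only, and not the cohorts' differences in age range, Harris Hip Score selection, imaging site and model source (CT versus CAD).

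This needs a few lines of analysis on existing data, with no new subjects or imaging. The drawback is that the wide intervals will make the result look less firm than bare means do.
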